The Multidisciplinary Association for Psychedelic Studies (MAPS) is a non-profit research and educational organization working as a clinical trial sponsor to obtain approval for the prescription use of 3,4-methylenedioxymethamphetamine (MDMA) as an adjunct to therapy in patients with posttraumatic stress disorder (PTSD). PTSD is a serious debilitating disorder that negatively impacts a person's daily life, and can result in diminished cognitive and psychosocial functioning, fractured relationships, inability to maintain employment, substance abuse, high-cost healthcare utilization, increased depression, and suicide risk. People who suffer from PTSD relive their traumatic experience(s) through nightmares and flashbacks, have difficulty sleeping, and feel detached or estranged. Symptoms can be severe and long lasting.

MDMA is a monoamine releaser and re-uptake inhibitor with indirect effects on neurohormone release. The combined neurobiological effects reduce defenses and fear of emotional injury, enhance communication and introspection, and increase empathy and compassion. MDMA may enhance fear extinction learning in humans. The subjective effects of MDMA create a productive psychological state that enhances the therapeutic process. Data from an international series of Phase 2 and 3 studies of MDMA-assisted therapy conducted by the sponsor provide preliminary evidence that chronic PTSD, independent of cause, is treatable with two to three sessions of MDMA-assisted therapy and associated non-drug preparatory and integrative therapy. This open-label safety extension study is intended to explore the safety and effectiveness of MDMA-assisted therapy for the treatment of PTSD.

Study Design

This multi-site open-label safety extension study of MDMA-assisted therapy for the treatment of participants with PTSD will be conducted in $N\approx 100$ participants, by invitation only.

The treatment consists of a flexible dose of MDMA, followed by a supplemental dose unless tolerability issues emerge, administered with therapy in three open-label approximately monthly Experimental Sessions. This Treatment Period is preceded by three Preparatory Sessions. During the Treatment Period, each Experimental Session is followed by three Integrative Sessions of non-drug therapy. Experimental Sessions are followed by an overnight stay; a sub-study (Appendix A) will assess feasibility of Experimental Sessions without an overnight stay. The Primary Outcome measure, the change in PCL-5 (PTSD Checklist for DSM-5) from Visit 3 is assessed at Visit 16. An independent Data Monitoring Committee (DMC) will review safety data as described in the DMC charter and at any time a Serious Adverse Reaction (SAR) occurs (refer to Section 10.5 Data Monitoring Committee).

For each participant, the study will consist of:

- **Screening Period**: phone screen, informed consent, eligibility assessment, and enrollment of eligible participants
- **Preparatory Period**: medication tapering, Preparatory Sessions
- **Treatment Period**: three monthly Experimental Sessions over up to 4 months, followed by Integrative Sessions
- Study Termination: Primary Outcome PCL-5 4 weeks after third Experimental Session
- Invitation to participate in Long-term Follow-up (LTFU) extension study: at least 6 months after last Experimental Session

Primary Outcome (PCL-5) Data Collection by Visit

PCL-5 Number	Visit	Description/Timing	
Initial PCL-5 T0	Screening	Prior to enrollment and initiation of tapering	
Baseline PCL-5 T1	V3	Baseline	
		After tapering and stabilization, at Preparatory Session 3 (Visit 3)	
PCL-5 T2	V6	10 to 18 days after Experimental Session 1	
		At Integrative Session 1.2 (Visit 6)	
PCL-5 T3	V10	10 to 18 days after Experimental Session 2	
		At Integrative Session 2.2 (Visit 10)	
PCL-5 T4	V14	10 to 18 days after Experimental Session 3	
		At Integrative Session 3.2 (Visit 14)	
Primary Outcome	V16	24 to 32 days after Experimental Session 3	
PCL-5 T5		At Study Termination (Visit 16)	

Dose Selection

This open-label study will examine the safety and effectiveness of a flexible dose of MDMA administered in three Experimental Sessions, as described in the table below, along with associated non-drug preparatory and integrative therapy. Similar MDMA doses to those proposed in this study have been safely used in previous Phase 2 and Phase 3 studies sponsored by MAPS.

Dose Regimen of MDMA

Experimental Session	Initial Dose	Supplemental Dose*	Min-Max Cumulative Dose
1	80 mg	40 mg	80 mg to 120 mg
2	80 or 120 mg	40 or 60 mg	80 mg to 180 mg
3	80 or 120 mg	40 or 60 mg	80 mg to 180 mg
	7	Total Cumulative Dose	240 mg to 480 mg

^{*} Unless tolerability issues emerge with the first dose or it is refused by the participant.

Protocol Objective

The overall objective of this study is to use standard clinical measures to explore the safety and effectiveness of MDMA-assisted therapy with a flexible dose of MDMA in reducing PTSD and associated symptoms.

Primary Objective

The primary objective of this study is to evaluate the effectiveness of MDMA-assisted therapy for PTSD, as measured by the reduction in PCL-5 total score from Visit 3 to Visit 16.

Secondary Objective

The key secondary objective of this study is to evaluate the effectiveness of MDMA-assisted therapy for PTSD in functional impairment, as measured by the mean change in Sheehan Disability Scale (SDS) item scores from Visit 3 to Visit 16.

Safety Objectives

The overall safety objective is to assess severity, incidence and frequency of Adverse Events (AEs), Treatment Emergent AEs (TEAEs), AEs of Special Interest (AESIs), and Serious Adverse Events (SAEs), concomitant medication use, suicidal ideation and behavior, and vital signs to support the package insert for MDMA-assisted therapy. The following safety objectives will evaluate the safety of MDMA-assisted therapy:

- 1. Assess incidence of AEs during Experimental Sessions that may be indicative of a medical complication of the Investigational Medicinal Product (IMP) such as clinical signs and symptoms of chest pain, shortness of breath, or neurological symptoms or any other signs or symptoms that prompt additional vital sign measurements
- 2. Assess incidence of AEs by severity
- 3. Assess incidence of TEAEs by severity
- 4. Assess incidence of TEAEs by severity reported during an Experimental Session, 1 day, and 2 days after IMP administration
- 5. Assess incidence of AESIs, defined as AEs specified in the protocol related to cardiac function, suicidality, and abuse liability
- 6. Assess incidence of AEs by severity categorized as leading to discontinuation of IMP, resulting in death or hospitalization, and continuing at Study Termination
- 7. Assess incidence of SAEs
- 8. Assess incidence of concomitant medications taken during an Experimental Session, 1 day, and 2 days after IMP administration
- 9. Assess incidence of psychiatric concomitant medications taken during the Treatment Period
- 10. Assess incidence of positive or serious suicidal ideation and positive suicidal behavior assessed with the Columbia Suicide Severity Rating Scale (C-SSRS)
- 11. Assess changes in blood pressure (BP), heart rate, and body temperature from pre-IMP administration to end of each Experimental Session

Recruitment and Participant Population

Approximately $N\approx100$ participants will be enrolled, by invitation only. Participants who were randomized to the placebo arm in the two parent Phase 3 trials and who meet all other entry criteria will be eligible and invited to participate in this open-label safety extension study. In addition, participants in the parent Phase 3 trials whose study participation was affected by the Coronavirus 2019 (COVID-19) global pandemic or other unforeseen circumstances, and were unable to complete the study (enrolled but not treated or enrolled, treated, but could not complete three Experimental Sessions prior to termination of the study) may participate in this open-label study if they meet all eligibility criteria and are approved by the Medical Monitor.

Participants will be 18 years or older, considered in good standing with the study site at which they enrolled in a parent study, and able to agree to lifestyle modifications. Participants would not be excluded for having more than one traumatic event or for having tried, not tolerated, or refused a selective serotonin reuptake inhibitor (SSRI) or serotonin norepinephrine reuptake inhibitor (SNRI) prescribed for PTSD. Participants must be in good physical health and without major medical disorders that could affect the safety or tolerability of MDMA.

Statistical Analyses

This is a multi-site open-label safety extension study of MDMA-assisted therapy for the treatment of participants with PTSD. The effectiveness of MDMA-assisted therapy will be measured by the PCL-5 and SDS. The sample size was not determined by statistical criteria. Every effort will be made to ensure (i) complete, accurate, and timely data collection and to avoid missing data, and (ii) the completeness of the data, which can impact the integrity and accuracy of the final study analysis. The statistical analyses will be reported using summary tables, figures, and data listings. All analyses and tabulations will be performed using SAS® Version 9.4. In general, nominal variables will be described in terms of frequencies and percentages. Ordinal and non-parametric continuous variables will be described using the sample median, 25th and 75th percentiles, and the interquartile range (IQR).

The following analysis set is defined for this study:

- All Enrolled: all participants who were enrolled in the study
- Safety: all participants who received any IMP

[figure not shown]
Primary Effectiveness Analysis

The primary analysis of the effectiveness of MDMA-assisted therapy will be made using a Mixed Model Repeated Measure (MMRM) model to assess changes in PCL-5 scores throughout the study period from Baseline (Visit 3) through Visit 16. Baseline covariates (age, gender, ethnicity, index trauma, complexity and severity of trauma, diagnosis of comorbid depression, diagnosis of comorbid Axis 2 diagnosis, adverse childhood experiences collected in the parent study) may be assessed for inclusion in the final model with an alpha level set at 0.05. Details of the analysis are described in the Statistical Analysis Plan.

Secondary Effectiveness Analysis

The SDS will be analyzed in a similar manner to the primary analysis of the PCL-5. Please refer to the Statistical Analysis Plan for more details.

Study Structure Overview

Protocol and Synopsis MAPPUSX IND #063384

A Multi-Site Open-Label Safety Extension Study of Manualized MDMA-Assisted Therapy for the Treatment of Participants with Posttraumatic Stress Disorder

CURRENT APPROVED

PROTOCOL

Amendment 2, Version 1, 06 July 2021

AMENDED PROTOCOL Amendment 3, Version 1, 15 March 2023

SPONSOR Multidisciplinary Association for Psychedelic Studies (MAPS)

[name]

SPONSOR

REPRESENTATIVE

[name]. Executive Director

MAPS

SPONSOR DELEGATE &TRIAL ORGANIZER

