1.2.3 MDMA-Assisted Therapy for PTSD

Many psychotherapies for PTSD involve the induction and extinction of abnormal autonomic responses through revisiting traumatic experiences in psychotherapy with an appropriate level of emotional engagement [20]. To be effective, exposure must be accompanied by a degree of emotional engagement or "fear activation" while avoiding dissociation or overwhelming emotion [41]. This has been referred to as working within the "optimal arousal zone" or "window of tolerance" [42-44].

The combined neurobiological effects of MDMA increase compassion, reduce defenses and fear of emotional injury, and enhance communication and introspection. MDMA produces anxiolytic and prosocial effects, which counteract avoidance and hyperarousal in the context of therapy. PTSD increases amygdala activity, causing heightened encoding of fearful memories and decreasing blood flow in the prefrontal cortex. In contrast, MDMA acutely decreases activity in the amygdala [45], and there is some indication that MDMA may increase activity in the prefrontal cortex [46]. Brain imaging after MDMA indicates less reactivity to angry facial expressions and greater reward in happy faces [45]. This action is compatible with its reported reduction in fear or defensiveness, and is in contrast to the stimulation of the amygdala observed in animal models of conditioned fear, a state similar to PTSD [47-49]. The reduction in stress-induced activation of the amygdala may be supported and enhanced by interacting with the therapy pair during and after the MDMA experience. The subjective effects of MDMA create a

productive psychological state that enhances the therapeutic process. MDMA is capable of inducing unique psychopharmacological effects, including decreased fear and increased wellbeing, sociability, interpersonal trust, acceptance of self and others, and ability to address these issues without extreme disorientation or ego loss due to alert state of consciousness. These factors taken together can provide the

MAPPUSX Protocol

Amendment 3 Version 1: 15 March 2023

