10.1.1 AE Definition

An AE is any untoward medical occurrence in a clinical study participant which does not necessarily have a causal relationship with the treatment. An AE can therefore be any unfavorable unintended sign, including an abnormal laboratory symptom or disease temporally associated with the use of IMP, whether or not related to the IMP.

Note: For the purpose of this study, an adverse event will be considered any event that occurs within the study, whether deemed positive, negative, or neutral by the investigator, qualified designee or reporter. Examples of positive or neutral events may include, but are not limited to:

Positive mood, calmness, talkative, elevated mood, dizziness, feeling abnormal, feeling drunk, feeling of relaxation, thinking abnormal, inappropriate affect, somnolence, mood disorders and disturbances, confusion and disorientation.

The investigator or qualified designee should carefully record any AE that occurs. Whenever possible, a diagnosis rather than a list of signs and symptoms is preferred. Treatment or intervention of an AE should not be reported as an event. The event necessitating the treatment or intervention should be reported. AEs should be followed until the events have subsided, returned to baseline or in case of permanent impairment, until the condition stabilizes.

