10.1.3 Adverse Events of Special Interest (AESI)

An adverse event of special interest (AESI) is a serious or non-serious event of scientific and medical concern specific to the study intervention. The event may require further investigation and depending on the nature of the event, submission to the FDA or other applicable regulatory authorities. For the purpose of this trial, AESIs have been predefined.

AESIs will be reported on the SAE/AESI report form within 24 hours of discovery. Any AESI that also meets the criteria of a SUSAR (suspected unexpected serious adverse reaction) will be emergently reported to FDA and other appropriate regulatory agencies, PIs, IRBs and IECs. AESIs will be followed until the outcome of the event is determined.

AESIs will include the following:

- Cardiac arrhythmias, or AEs that are indicative of QT interval prolongation, including (but not limited to) Torsade de pointes, sudden death, ventricular extrasystoles, ventricular tachycardia, ventricular fibrillation and flutter, palpitations, and non-postural syncope
- Cardiac disorders (e.g., acute MI, angina pectoris, ischemic chest pain)
- Drug diversion, drug abuse and drug accountability (e.g., accidental poisoning, behavioral
 addiction, dependence, drug abuser, drug diversion, overdose, intentional overdose, intentional
 product misuse, poisoning deliberate, prescribed overdose, substance abuser, euphoria-like
 response, hallucination dissociative state, psychosis, aggression, drug tolerance, habituation, drug
 withdrawal syndrome, substance related disorders)

- Central nervous system vascular disorders (e.g., ischemic central nervous system vascular)
- Seizures
- Hypertensive crisis

conditions)

• Suicide, suicidal behavior (e.g., intentional overdose, intentional self-injury, suicide attempt, suicide threat, suspected suicide, suspected suicide attempt), C-SSRS Suicidal Ideation score of 4 or 5, and/or suicidal ideation judged to be serious or severe in the opinion of the investigator

MAPPUSX Protocol

Amendment 3 Version 1: 15 March 2023

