### **8.8.2 Analysis of Adverse Events**

The primary measure of safety will be the reporting of unsolicited AEs. All AEs collected from Enrollment to Termination will be categorized as follows:

- Pretreatment AEs are defined as AEs that occur during the Preparatory Period prior to the first dose in the first Experimental Session
- Treatment Emergent AEs are defined as AEs that occur during the Treatment Period from the first Experimental Session to the last Integrative Session
- AEs that occur on and two days after MDMA administration
- AESIs are defined as AEs specified in the protocol related to cardiac function and abuse liability
- Follow-up Period AEs are defined as AEs that occur during the Follow-up Period after the last Integrative Session through Termination
- AEs leading to discontinuation of IP
- AEs resulting in death or hospitalization.
- SAEs
- AEs continuing at Termination.

Verbatim terms on case report forms will be mapped to preferred terms (PT) and system organ class (SOC) using the Medical Dictionary for Regulatory Activities (MedDRA) Version 24.0. Frequency and incidence of AEs will be displayed by PT, sorted by SOC, severity, and seriousness. AEs will be analyzed and presented as follows:

- If a participant has more than one AE mapped to the same PT, that AE will be reported once using the highest severity
- Relationship will be determined by the Clinical Investigator
- AEs that occur on day of Experimental Sessions and two days after IP administration will be presented separately.

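### Positive and neutral effects count as adverse events and no listed item or planned table marks them, so pooled AE and TEAE incidences mix intended drug effects with harm; the abuse-liability AESI boundary is also undefined

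*Protocol*

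**What the plan says.** - **Objective.** The protocol synopsis says: "The overall safety objective is to assess severity, incidence and frequency of Adverse Events (AEs), Treatment Emergent AEs (TEAEs), AEs of Special Interest (AESIs" and others). Protocol 2.3 and the synopsis set out incidence objectives for AEs, TEAEs and AESIs, several of them by severity. One covers TEAEs on the session day and the two days after. SAP 8.8.2 adds: "The primary measure of safety will be the reporting of unsolicited AEs".
- **Definition.** Protocol 10.1.1 opens with "An AE is any untoward medical occurrence in a clinical study participant". A study-specific note then extends this to "any event that occurs within the study, whether deemed positive, negative, or neutral by the investigator". The examples of positive or neutral events begin "Positive mood, calmness, talkative, elevated mood, dizziness, feeling abnormal, feeling drunk, feeling of relaxation, thinking abnormal, inappropriate affect, somnolence" and go on to mood disturbances, confusion and disorientation.
- **Intended effects.** Protocol 1.2.3 describes the sought effects of MDMA as "including decreased fear and increased wellbeing, sociability, interpersonal trust, acceptance of self and others". Protocol 4.6 expects the initial doses to produce all the commonly reported effects.
- **Recorded items.** Protocol 10.1 lists seriousness, AESI class, description, severity, relationship, action taken, outcome, and onset and stop dates. It mentions events being deemed positive, negative or neutral, but the list has no item for that judgement.
- **Tabulation.** SAP 8.8.2 displays AEs by preferred term, SOC, severity and seriousness. Repeat events under one preferred term in a participant count once, at the highest severity.
- **AESIs.** The drug-abuse category in protocol 10.1.3 includes "prescribed overdose, substance abuser, euphoria-like" response alongside diversion, dependence, overdose and withdrawal.

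**The concern.** Calmness, relaxation and positive mood are AEs under the note in 10.1.1, and they overlap with what 1.2.3 presents as the therapeutic action. A headline such as the percentage of participants with any TEAE then answers a question about drug activity as much as one about harm. A reader of a package insert would normally take it as harm. The session-day and two-day TEAE incidences are the most exposed, because protocol 1.2.2 puts the effects of the initial dose at 3 to 6 hours.

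Because AEs are unsolicited and elicited by open-ended questions, the pooled rate also depends on how readily each site writes down a pleasant effect.

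The abuse-liability AESI has a related weakness. Elevated mood is an example of a positive or neutral AE, a euphoria-like response is an AESI reportable within 24 hours, and no rule divides the two.

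**Working it through.** The plan states no figure to reproduce: the sample size of about 100 has no statistical basis and no expected AE rate is given. The check is therefore textual, followed by an illustration on assumed rates.

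**1. Can another listed item stand in for the missing judgement?**

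| Listed item | What it carries | Does it separate wanted from unwanted? |
|---|---|---|
| Relationship (10.1.1.2) | Attribution, yes or no | No. Intended effects are also related |
| Severity (10.1.1.1) | Limitation of daily activity | Partly. A pleasant effect with no limitation is mild, so the mild row is diluted most. Moderate and severe are partly protected |
| Description, coded to preferred term | The event's name | Yes for plainly positive terms (calmness, positive mood). No for dizziness, somnolence, confusion or feeling abnormal, which 10.1.1 lists as positive or neutral but which can also be harms |
| Seriousness, action taken, outcome | Consequences | Yes for SAEs, discontinuations and hospitalisations |

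For the ambiguous terms, the highest-severity rule in SAP 8.8.2 can also merge a benign and a harmful occurrence under one preferred term within a participant.

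**2. Which summaries are affected?** Those that add across preferred terms: any AE, any TEAE, any related TEAE and SOC-level incidence, and by-severity incidence to a lesser extent. Little affected: preferred-term rows for clear terms, SAEs, AEs leading to discontinuation, AEs resulting in death or hospitalisation, and cardiac AESIs.

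**3. How could pooling hide a difference in harm?** Assumptions, none from the documents: h is the proportion of participants with a harmful AE, p is the chance per session that a positive or neutral effect is recorded, there are three sessions, and all are independent. Then any-AE incidence is

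A = 1 − (1 − h)(1 − p)³

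| p | h = 20% | h = 40% | h = 60% |
|---|---|---|---|
| 0.1 | 41.7% | 56.3% | 70.8% |
| 0.3 | 72.6% | 79.4% | 86.3% |
| 0.5 | 90.0% | 92.5% | 95.0% |
| 0.8 | 99.4% | 99.5% | 99.7% |

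For p = 0.5, (1 − p)³ = 0.125. So h = 20% gives 1 − 0.8 × 0.125 = 90.0%, and h = 60% gives 1 − 0.4 × 0.125 = 95.0%. With N = 100, the 95% half-width at 90% is 1.96 × √(0.9 × 0.1 / 100) = 5.9 points. Tripling the harm rate moves the pooled incidence by 5 points, which is less than that half-width.

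Without the independence assumption, pooled data bound h only between max(0, A − q) and A, where q = 1 − (1 − p)³. At p = 0.5 and A = 90.0%, q = 87.5% and the bounds are 2.5% to 90.0%. At p = 0.1 the pooled figure still tracks harm reasonably well (41.7% to 70.8%). The result turns on p, which the documents do not give.

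**4. The AESI category.** Protocol 10.1 has AESI class recorded for each event. 10.1.1 and 10.1.3 name neighbouring mood terms with no rule between them, and the category then pools acute effects with diversion, abuse, dependence and withdrawal.

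**The case against.** **Broad capture is deliberate.** The note in 10.1.1 is openly study-specific, and Table 9 in protocol 9.1 says the FDA asked for consistent monitoring of events suggestive of abuse potential. Euphoria-like effects are part of that signal. This stands: nothing should be dropped from collection. It does not justify leaving the term boundary undefined or showing acute effects only in one pool with misuse.

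**The data are not blind to harm.** A reader might infer that harm and drug effect cannot be separated at all. The documents do not support that, because preferred-term display and the separate SAE, discontinuation, death and hospitalisation categories do much of the work.

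**The case report form is not among the documents.** A reader might infer that the judgement is stored nowhere and no split could ever be made. All that can be said is that the 10.1 list omits it. Verbatim descriptions are kept and coded, so some later classification is possible, though it is weak for ambiguous terms.

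**No size can be claimed.** A reader might infer that any-TEAE incidence must approach 100%, or that abuse-liability AESI incidence could lie anywhere from none to nearly all. The rationale describes pharmacology. It does not say how often such effects will be recorded.

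**Filtering could do harm of its own.** A reader might conclude that the main tables should be limited to unfavourable events. The study is open-label, and Table 9 treats therapy-related discomfort as a necessary part of treatment. An investigator could mark distress as neutral or positive and so remove it from view. This objection stands and shapes the fix.

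**Conclusion.** The point holds for pooled summaries. Any-AE, any-TEAE, related-TEAE and SOC-level incidences, and by-severity incidences to a lesser extent, mix intended effects with harm, and neither the recorded items in protocol 10.1 nor SAP 8.8.2 provides a way to show them apart. It does not extend to the preferred-term rows for clear terms or to the SAE, discontinuation, hospitalisation and cardiac AESI results.

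The size cannot be estimated from the documents. The illustration shows only that the pooled figure can become uninformative if positive or neutral effects are recorded in about half of sessions or more, and that it stays informative if they are rarely recorded.

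For abuse-liability AESIs the defect is narrow: an undefined boundary between two mood terms, and one category holding both acute effects and misuse. No hypothesis test depends on any of this. It is an inexpensive improvement to the primary safety measure and does not invalidate the safety assessment.

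**What to change.** 1. **Protocol 10.1.1:** reconcile the untoward definition with the note, stating that the note extends the standard definition for this study.
2. **Protocol 10.1:** keep recording all events and add one item, judged at recording: unfavourable, positive or neutral.
3. **SAP 8.8.2:** keep the all-events tables as the main tables. Add supplementary AE, TEAE, related-TEAE and severity tables by the new item, with events lacking the judgement shown as not classified.
4. **SAP 8.8.2:** add an abuse-potential table from a fixed list of MedDRA preferred terms, applied to all AEs whatever the site's AESI flag. Show acute psychoactive effects on session days separately from misuse, diversion, dependence and withdrawal.

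Cost: one case report form field, a term list and some extra tables. The judgement is partly subjective in an open-label study. Since this is already Amendment 3, it may also be missing for events already collected. For both reasons it must not filter the main tables.
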